8.5.2. Presentation of Pharmacokinetic Data

All PK concentrations and parameters will be listed.

Summary tables, arithmetic mean (+ standard deviation [SD]) figures, overlaying individual figures, and individual figures by treatment and time postdose will be provided for plasma PK concentrations. All figures will be produced on both linear-linear and linear-logarithmic scales, with the exception of figures across all days, which will be produced on the linear-linear scale only. The +SD bars will only be displayed on the linear-linear scale.

Summary tables by treatment will be provided for all PK parameters, with the exception of diagnostic regression-related PK parameters. Separate summary tables by treatment and time interval will be provided for excretion parameters and cumulative excretion parameters.

A subject may be excluded from the PK summary statistics and statistical analysis if the subject has an AE of vomiting that occurs at or before 2 times the median t_{max} .

Any exclusions from PK summary statistics and/or statistical analysis will be identified by pharmacokineticist and will be agreed with AnaMar AB.

If the actual time of sample collection deviates from the nominal time by more than $\pm 10\%$, the concentration will be flagged and excluded from summary statistics. Individual concentrations that are deemed to be anomalous will be flagged in the listings and excluded from the summary statistics.

For PK concentration data the following rules will apply:

- Values that are BLQ will be set to 0 for the calculation of summary statistics.
- Arithmetic mean or median values that are BLQ will be presented as 0.

For PK parameters the following rule will apply:

• Geometric mean and coefficient of variation (CV) will not be calculated for t_{last} and $t_{max}.$

8.5.3. Pharmacokinetic Statistical Methodology

8.5.3.1. Dose Proportionality Assessment

A statistical analysis will be conducted to investigate the dose proportionality of AUC_{0-tlast}, AUC_{0- ∞}, and C_{max} on profile day 1 for Part A and AUC_{0- τ} and C_{max} on profile day 10 for Part B (only for plasma AM1476).

The PK parameters will be analysed using a power model⁴ that will have the following form:

parameter = *intercept* × *dose*^{*slope*} × *random error*

Using the natural log (ln) transformation,⁵ a power model can be expressed as a linear regression equation:

 $ln(parameter) = intercept + slope \times ln(dose) + random error$

For dose proportionality, the slope of the regression line is equal to 1; for dose independence, it is equal to 0.

For each PK parameter separately, a pooled estimate (across all doses) of slope, corresponding 95% confidence interval (CI), and between-subject CV will be calculated. Figures (on the logarithmic-logarithmic scale) containing individual values, power model line (95% CI), and dose proportionality line (defined as the power model line with slope of 1) will be created for each PK parameter. Additionally, figures (on the logarithmic-linear scale) containing individual values and geometric means will be created for each corresponding PK parameter normalised by dose administered.

The lack of fit test will be conducted for the statistical assessment of linearity assumption, and thus appropriateness of a power model. The lack of fit model will be the same as the power model fitted, but with dose included as additional fixed effect. The statistical assessment will rule the linearity assumption acceptable if the diagnostic plots appear reasonable and the lack of fit 2-sided p-value >0.05 (dose effect is not significant at the 0.05 level of significance). The assessment of linearity assumption may also occur via visual examination of the figures by the pharmacokineticist. This assessment may override the statistical assessment; where this occurs, it will be detailed in the CSR.

It will be concluded that PK parameter is dose proportional for the dose range studied if the assumption of linearity is ruled acceptable and the 95% CI for the slope spans 1.

If the assumption of linearity is ruled unacceptable for any PK parameter, its corresponding PK parameter normalised by dose administered will be ln-transformed and analysed using an analysis of variance (ANOVA) model.⁶ The model will include dose as a factor.

For each PK parameter separately, the geometric least squares mean (GLSM) for each dose, p-values for the overall, and pairwise dose comparisons will be calculated. Residual plots will be produced to assess the adequacy of the model(s) fitted.

Examples of the SAS code that will be used are as follows:

SAP Covance Study: 8417263

Power Model Analysis

```
proc mixed data = <data in> alpha = 0.05;
by parcatln parcatl pkday paramn param;
model lpk = ldose / cl residual ddfm = kr2;
ods output solutionf = <data out>;
run;
```

Power Model Analysis (Between-subject Variability)

```
proc mixed data = <data in> covtest alpha = 0.05;
by parcatln parcatl pkday paramn param;
class ldose;
model lpk = ldose / cl residual ddfm = kr2;
ods output covparms = <data out>;
run;
(Note: Pooled Geometric CV (%) = 100*(sqrt(exp(estimate)-1)))
```

Power Model Analysis (Lack of Fit Test)

```
proc mixed data = <data in>;
by parcat1n parcat1 pkday paramn param;
class dose;
model lpk = ldose dose / htype = 1 ddfm = kr2;
ods output tests1 = <data out>;
run;
```

ANOVA Model Analysis

```
proc mixed data = <data in> alpha = 0.05;
by parcatln parcatl pkday paramn param;
class dose;
model ldnpk = dose / cl residual ddfm = kr2;
lsmeans dose / cl pdiff;
ods output lsmeans = <data out>;
ods output diffs = <data out>;
ods output tests3 = <data out>;
run;
```

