For predicted non-pharmacologically active dose levels, dose levels should not increase such that the maximum exposure (as assessed by  $C_{max}$  and/or AUC0-24) is predicted to increase by > 5-fold for any individual subject. For predicted pharmacologically active dose levels, dose levels should not increase such that the maximum exposure (as assessed by  $C_{max}$  and/or AUC0-24) is predicted to increase by > 3-fold for any individual subject. Exposures will be planned to not exceed that stated in the dose escalation stopping criteria (Section 3.7). Exposure will be assumed to increase in a dose-proportional manner until there is sufficient PK data available to suggest PK is not linear.

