3.2. Secondary Endpoints

For Part A, the single-ascending dose and food (fed versus fasted dietary status at dosing), PK outcome endpoints of AM1476 are as follows:

- area under the concentration-time curve from time 0 to infinity $(AUC_{0-\infty})$
- area under the concentration-time curve from time 0 to the time of the last quantifiable concentration (AUC_{0-tlast})
- maximum observed concentration (C_{max})
- time of the maximum observed concentration (t_{max})
- apparent terminal elimination half-life $(t_{\frac{1}{2}})$
- apparent total clearance (CL/F)
- apparent volume of distribution (V_z/F)
- renal clearance (CL_R)
- amount of the dose administered recovered over the time interval t1 to t2 (Ae_{t1-t2})
- percentage of the dose administered recovered over the time interval t1 to t2 (Fe_{t1-t2}).

For Part B, the multiple-ascending dose PK outcome endpoints of AM1476 are as follows:

- area under the concentration-time curve over a dosing interval $(AUC_{0-\tau})$
- $AUC_{0-\infty}$ (Day 1 only)
- C_{max}
- minimum observed concentration (C_{min})
- t_{max}
- t¹/₂
- CL/F
- V_z/F
- observed accumulation ratio based on AUC_{0- τ} (RA_{AUC0- τ})
- observed accumulation ratio based on C_{max} (RA_{Cmax})
- CL_R
- Ae
- Fe.

Other PK parameters may also be reported.

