8. STATISTICAL METHODOLOGY

8.1. General

Listings will be provided for all data captured in the database, with the exception of medical history. Listings will include all subjects assigned to the all subjects population and include data up to the point of study completion or discontinuation. Subjects are generally considered to have completed the study if they complete the scheduled follow-up visit (rather than early termination visit). Any subject who discontinues the study will be identified accordingly in the listings. Summaries and statistical analyses will include the subjects assigned to the relevant population based on data type.

Analysis Data Model (ADaM) datasets will be prepared using Clinical Data Interchange Standards Consortium (CDISC) ADaM Version 2.1 (or higher if a new version is issued during the study) and CDISC ADaM Implementation Guide Version 1.1 (or higher if a new version is issued during the study). Pinnacle 21 Community Validator Version 3.0.2 (or higher if a new version is issued during the study) will be utilised to ensure compliance with CDISC standards.

For all statistical analyses, the hypothesis testing will be 2-sided and carried out on 0.05 significance level, unless specifically stated otherwise.

Caution should be used when interpreting results from the statistical analyses conducted in this study because the sample size is not based on power calculations.

Where reference is made to 'valid' data, this refers to non-missing data which meet the predetermined criteria (eg, are not flagged for exclusion).

Where reference is made to 'all calculations', this includes, but is not limited to, summary statistics, statistical analyses, baseline derivation, and changes from baseline.

All figures will be produced on linear-linear or discrete-linear scales, as applicable, unless specifically stated otherwise.

8.1.1. Handling of Data Quality Issues Due to Coronavirus Disease 2019 and Related Restrictions

Due to COVID-19 and related restrictions, there is a high risk for impact to data integrity, with the recognised potential for:

- Missed visits, caused by, for example:
 - Subject unable to travel to site due to restrictions, the need to quarantine, or COVID-19 infection
 - o Subject unwilling to go to site due to fear of COVID-19 infection
 - Site postponing subject's visit due to investigator not being available (eg, if they have been dispatched to hospital handling COVID-19 infections)

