8.5.1.2. Criteria for Calculation and Reporting of Area Under the Concentration-time Curve

The minimum requirement for the calculation of area under the concentration-time curve (AUC) will be the inclusion of at least 3 consecutive concentrations above the lower limit of quantification (LLOQ). If there are only 3 consecutive concentrations, at least 1 should follow C_{max} .

If the extrapolated area is >20%, AUC_{0- ∞} (and derived parameters) may be excluded from summary statistics and statistical analysis at the discretion of the sponsor or pharmacokineticist.

If $AUC_{0-\infty}$ cannot be determined reliably for all subjects and/or dose levels, an alternative AUC measure, such as AUC to a fixed timepoint or $AUC_{0-tlast}$, may be used in the statistical analysis of dose proportionality/food-effect.

If the end of the dosing interval PK blood sample is collected slightly early (ie, the 24 hour sample), the actual sampling time of the scheduled τ sample (24 hours) may be used for the

calculation of AUC_{0- τ}. However, the AUC_{0- τ} parameter will be calculated if the τ sample is within 60 minutes of the nominal sampling time.

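### AUC0-tlast in the Part A dose-proportionality model covers an interval that can lengthen with dose, so its slope can be biased upward for a linear drug if low-dose profiles fall below the assay limit early

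*SAP*

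**What the plan says.** SAP 8.5.3.1: "A statistical analysis will be conducted to investigate the dose proportionality of" AUC0-tlast, AUC0-inf and Cmax in Part A, and AUC0-tau and Cmax on Day 10 in Part B. The analysis is a regression of ln(parameter) on ln(dose): "For each PK parameter separately, a pooled estimate (across all doses) of slope, corresponding 95% confidence interval" and a CV are reported. Linearity is accepted if diagnostic plots look reasonable and "the lack of fit 2-sided p-value >0.05", although the pharmacokineticist may override this. Proportionality then requires that "the 95% CI for the slope spans 1". If linearity is rejected, an ANOVA is run on the dose-normalised form of the same parameter. SAP 8.1 sets the general standard: "the hypothesis testing will be 2-sided and carried out on 0.05 significance level".

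SAP 3.2 defines AUC0-tlast as "area under the concentration-time curve from time 0 to the time of the last quantifiable concentration". Under SAP 8.5.1.4, values below the LLOQ after the first measurable one count as missing. Part A sampling ends at 48 h (Protocol Appendix 6).

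SAP 8.5.1.2 lets AUC0-inf be left out of the analysis, at discretion, when more than 20% of it is extrapolated. If AUC0-inf is unreliable, "an alternative AUC measure, such as AUC to a fixed timepoint or" AUC0-tlast may be used, with no order of preference between the two.

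Protocol 8.3 also names AUC0-tlast for dose proportionality. The starting dose is 1 mg and later doses are to be determined (Protocol Table 6). Protocol 3.6 limits a step so that Cmax and/or AUC0-24 in the predicted pharmacologically active range never "is predicted to increase by > 3-fold for any individual subject". The limit is 5-fold below that range. AUC0-24 is not in the SAP's Part A parameter table.

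**The concern.** A power-model slope has a clear meaning only if the response is the same quantity at every dose. AUC0-tlast need not be. Where the assay loses the drug early at low doses and follows it to 48 h at high doses, the low-dose AUC omits a larger share of the true exposure, and the slope rises for a reason that is analytical rather than pharmacokinetic.

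The decision rule has no tolerance margin, so a small systematic shift can change the result. It can do so in two directions: a linear drug may fail, or a true slope below 1 may be pushed back towards 1. The second matters because Protocol 1.7 reports less-than-proportional exposure at higher doses in animals.

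The later steps do not remove the problem. The ANOVA uses the same AUC0-tlast divided by dose. The fallback in SAP 8.5.1.2 can bring in AUC0-tlast exactly where truncation is heaviest, since early truncation and large extrapolation occur in the same low-dose profiles.

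**Working it through.** **No figure to reproduce.** The plan gives no expected slope, power or precision for this analysis.

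**Inputs from the documents:** the Part A sampling times (0.25 to 48 h), 6 active subjects in each of 6 groups, a 1 mg start, linear-up/log-down AUC, the LLOQ rule above, and the 95% interval rule.

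**Assumptions, not in the documents:** strictly linear one-compartment oral kinetics, ka 2/h, half-life 3, 8 or 15 h, 1 mg Cmax of 3 to 50 times the LLOQ, between-subject CV 20-40%, assay noise 8%, and illustrative dose ranges of 1-243 mg (3-fold steps) and 1-32 mg (2-fold steps). The ranges serve the arithmetic only.

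**One case by hand** (half-life 8 h, 1 mg Cmax = 3 x LLOQ, 1-243 mg). Take concentrations in units of (1 mg)/V:

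- ke = ln 2 / 8 = 0.0866, and ka/(ka - ke) = 2/1.9134 = 1.0453.
- C(t) = dose x 1.0453 x (exp(-ke t) - exp(-ka t)). At 1 mg the largest sampled value is 0.866 (1.5 h), so LLOQ = 0.866/3 = 0.289.
- Share of true AUC captured: f = 1 - 1.0453 x exp(-ke x tlast).

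| Dose (mg) | Last value at or above 0.289 | Next sample | tlast (h) | f |
|---|---|---|---|---|
| 1 | 0.370 | 0.261 | 12 | 0.630 |
| 3 | 3 x 0.1307 = 0.392 | 3 x 0.0462 = 0.139 | 24 | 0.869 |
| 9 | 9 x 0.0462 = 0.416 | 9 x 0.0163 = 0.147 | 36 | 0.954 |
| 27, 81, 243 | 27 x 0.0163 = 0.441 and above | none | 48 | 0.984 |

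The excess slope is the regression of ln f on ln dose. With doses at -2.5 to +2.5 steps of ln 3 = 1.0986, the sum of squares is 17.5 and the sum of cross-products is 1.313. So the excess is 1.313/(17.5 x 1.0986) = 0.068. The true slope is 1 and the AUC0-tlast slope is **1.068**.

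**Simulated results under a true slope of 1** (120 to 400 trials per scenario). The last three columns give the share of trials with the lower 95% limit above 1 (nominal 2.5%):

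| Range, half-life, 1 mg Cmax/LLOQ | Noise-free slope | CV 20% | CV 30% | CV 40% |
|---|---|---|---|---|
| 1-243 mg, 8 h, 3 | 1.068 | 81% | 54-58% | 35% |
| 1-243 mg, 8 h, 5 | 1.048 | 49% | 27-37% | 23% |
| 1-243 mg, 8 h, 10 | 1.019 | 17% | 8-11% | 9% |
| 1-243 mg, 3 h, 3 | 1.058 | 73-74% | 46-50% | 37% |
| 1-32 mg, 8 h, 3 | 1.127 | - | 52% | - |

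With a 15 h half-life and a ratio of 10 or more, every dose reaches 48 h and the slope is 1.000. With a ratio of 20 or more, slopes are 1.000-1.017 and the share is 2-7%.

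**Masking.** A true slope of 0.93 plus a bias of 0.068 gives about 0.998. In a simulation with a true slope of 0.93, AUC0-tlast detected the departure in 71% of trials when truncation was negligible and in 6% in a heavily truncated case. That case assumed a slow second phase (5% coefficient, 12 h half-life), LLOQ 1 ng/mL and 1 mg Cmax 8.30 ng/mL. The 8.30 is the first value in Protocol Table 3, whose row labels are lost here, so reading it as Cmax is itself an assumption.

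**Other parameters.** AUC0-inf gave mean slopes of about 0.98-1.00, with the interval excluding 1 in about 2-10% of runs. In the hand-worked case, however, its extrapolated share at 1 mg is 1 - 0.630 = 37%, above the 20% threshold.

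**Common interval.** With AUC from 0 to the lowest dose's tlast, the noise-free slope is 1.0000 in all six scenarios tried, and the lower limit exceeds 1 in 2.0-3.7% of trials at CV 30%. This calculation treated every value inside the window as measured, so it does not test any rule for subjects who fall below the LLOQ within it.

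**The case against.** The strongest reply is that nothing in the documents shows that truncation will occur. LLOQ, human half-life, CV and every dose above 1 mg are absent. With a sensitive assay or a long half-life the effect vanishes. A reader might infer that 1 mg profiles will certainly be cut short; the documents do not support that.

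A reader might also infer that the drug would be declared non-proportional. The SAP concludes per parameter, has no rule that turns one result into a verdict on the drug, and tests AUC0-inf and Cmax alongside. Nor is AUC0-tlast bound to become the only AUC left. Excluding AUC0-inf is discretionary, a fixed-timepoint AUC is already permitted, and Cmax remains.

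The plan has further safeguards. SAP 8.1 warns that results need caution because sample size was not based on power. tlast is a Part A parameter and will be summarised by treatment, so drift would be visible. Additional parameters may be calculated. The absence of AUC0-24 is not in itself a fault in the test: Protocol 3.6 uses it for predicted exposure in escalation, and the final analysis need not use the same measure.

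Finally, Protocol 8.3 specifies AUC0-tlast, and a short common window could miss non-linearity in late elimination. In one re-run at LLOQ 1 ng/mL the window was 4-6 h and held about 73-82% of AUC0-48.

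These points limit the size and reach of the concern, and the last argues against deleting AUC0-tlast. They do not answer the core of it: the plan has no common interval, no statement of which parameter prevails, and no preference for the fixed-timepoint AUC over AUC0-tlast in the fallback.

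**Conclusion.** The concern holds as a conditional one. If low-dose profiles fall below the LLOQ well before 48 h, the AUC0-tlast slope is biased upward under exactly linear kinetics, and the interval rule can then fail a linear drug on that parameter or conceal a true slope below 1.

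For 1-243 mg at CV 30%, the slope runs from about 1.00 to 1.07. The interval excludes 1 in about 5% of trials when 1 mg Cmax is about 20 times the LLOQ or more, rising to about 60% at about 3 times, against a nominal 5%. These figures rest on the assumed kinetics, CV and dose range.

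The artefact belongs to one of three parameters tested in parallel for a secondary objective. Its practical weight comes from the missing order of precedence and from the fallback. Part B uses a fixed dosing interval and is not affected.

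**What to change.** 1. **SAP 8.5.3.1 and the Part A parameter table.** Add an AUC over one nominal interval common to all dose groups: AUC0-24 if the 24 h sample is quantifiable in most subjects at every dose, otherwise AUC to the latest nominal time quantifiable in most subjects at the lowest dose. Fix the window without reference to the slope results, and state how subjects who fall below the LLOQ inside it are handled.
2. **SAP 8.5.3.1.** Keep AUC0-tlast as supportive only, and report tlast by dose beside its slope. State that AUC0-inf prevails if results disagree, or the common-interval AUC when AUC0-inf is unreliable.
3. **SAP 8.5.1.2.** Remove AUC0-tlast as the dose-proportionality fallback, leaving the fixed-timepoint AUC.
4. **SAP Section 10.** Record the change, since Protocol 8.3 gives AUC0-tlast equal standing and the section now reports no significant changes.

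The cost is one more parameter derived from samples already planned, SAP wording, and a documented departure from the protocol analysis. If 1 mg profiles prove short, the common window will reflect mainly early exposure, and the report should say so.

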#### 1.7. Summary of Non-clinical Pharmacokinetics

[figure not shown]
Generally, sex differences in  $C_{max}$  and  $AUC_{0-24}$  values were less than 2-fold. Exposure, as assessed by  $C_{max}$  and  $AUC_{0-24}$ , generally increased with the increasing dose level. The increases in  $C_{max}$  and  $AUC_{0-24}$  were approximately dose-proportional at lower dose levels and less-than-dose-proportional at higher dose levels. Overall, there was no accumulation of AM1476 observed after multiple doses in both mice and dogs, except after multiple administrations of 65 mg/kg/day in the dog.

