#### 1.9. Study Rationale

This is the first time AM1476 will be administered to humans. The principal aim of this study is to obtain safety and tolerability data when AM1476 is administered orally as single and multiple doses to healthy subjects. This information, together with the pharmacokinetic (PK) data, will help establish the doses and dosing regimen suitable for future studies in patients. The study will also investigate the effect of food on the PK of AM1476 prior to patient studies.

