5. SAMPLE SIZE JUSTIFICATION

No formal statistical assessment, in terms of sample size, has been conducted as this is the first time AM1476 is being administered to humans. However, the number of subjects in each part of the present study is common in early clinical pharmacology studies and is considered sufficient to achieve the objectives of the study.

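### The SAP reports failure to reject a slope of 1 as a positive conclusion of dose proportionality

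*SAP*

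**What the plan says.** SAP 8.5.3.1 regresses the log PK parameter on log dose and estimates the slope with a 95% CI, for AUC0-tlast, AUC0-∞ and Cmax in Part A and for AUC0-τ and Cmax on Day 10 in Part B. It then fixes a verdict: the parameter is concluded to be "dose proportional for the dose range studied if the assumption of linearity is ruled acceptable and the 95% CI for the slope spans 1".

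The linearity condition is met if the diagnostic plots look reasonable and the "lack of fit 2-sided p-value >0.05". The pharmacokineticist may also judge linearity from the figures, and "This assessment may override the statistical assessment". If linearity is rejected, dose-normalised values go to an ANOVA.

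Protocol 8.3 names the power model or ANOVA but gives no decision rule, so the rule originates in the SAP. On precision, SAP 5 says "No formal statistical assessment, in terms of sample size, has been conducted", and SAP 8.1 asks for caution because "the sample size is not based on power calculations".

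**The concern.** A 95% CI that contains 1 is the same event as not rejecting slope = 1 at two-sided 0.05. The SAP turns that into a positive statement. The linearity condition in front of it is also a failure to reject, so both steps are easier to pass when the data are noisy. If the true slope is 1, the CI spans 1 in 95% of trials whatever the variability. If it is not 1, the chance of the wrong conclusion rises with variability and with a narrower dose range.

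A departure is plausible here. Protocol 1.7 describes animal exposure as "approximately dose-proportional at lower dose levels and less-than-dose-proportional at higher dose levels". PK is a secondary objective, and Protocol 1.9 says the PK data, together with the safety data, "will help establish the doses and dosing regimen suitable for future studies in patients". An unsupported statement of proportionality in the study report could carry into exposure predictions for those studies.

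**Working it through.** The plan states no power, margin or error rate for this analysis, so there is no figure to reproduce. The question is how often the rule returns 'dose proportional' when exposure is not proportional.

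**Inputs from the documents.** Six active subjects per group: 6 × 6 = 36 in Part A and 3 × 6 = 18 in Part B (SAP 4.1, 4.2). Two-sided 5% level and 95% CI (SAP 8.1, 8.5.3.1).

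**Assumed, because the documents do not give them.** Between-subject CV of 20, 30, 40 and 50%; Part B doses in ratio 1:2:4; Part A doses equally spaced on the log scale; the size of each departure.

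**Formulas.** σ = √ln(1 + CV²); SE(slope) = σ/√Sxx. P(CI spans 1) comes from the noncentral t distribution with N − 2 df. The joint event (lack-of-fit p > 0.05 and CI spans 1) was simulated with at least 100,000 trials per scenario. The fold departure over a dose range r is r^(slope − 1).

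**Part B.** Sxx = 6 × 2 × (ln 2)² = 5.77 and df = 16. At CV 30%, σ = √ln(1.09) = 0.294, SE = 0.294/2.40 = 0.122 and the half-width is 2.12 × 0.122 = 0.26. A slope of 1.3 or 0.7 means 4^0.3 = 1.52-fold or 4^(−0.3) = 0.66-fold at the top dose. A slope of 1.5 means 4^0.5 = 2-fold.

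| Part B, 1:2:4 | CV 20% | 30% | 40% | 50% |
|---|---|---|---|---|
| SE(slope) | 0.082 | 0.122 | 0.160 | 0.197 |
| 95% CI half-width | 0.17 | 0.26 | 0.34 | 0.42 |
| CI spans 1, slope 1.3 or 0.7 | 7% | 37% | 58% | 70% |
| Both conditions, slope 1.3 or 0.7 | 7% | 35% | 55% | 66% |
| CI spans 1, slope 1.5 | 0% | 3% | 17% | 33% |

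With a true slope of exactly 1, both conditions are met about 90% of the time. The lack-of-fit test therefore adds little protection against a log-linear departure.

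**Part A.** Two patterns behave very differently.

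| Part A, 6 doses | CV 20% | 30% | 40% | 50% |
|---|---|---|---|---|
| CI spans 1, slope 1.2, 100-fold range | 0% | 0% | 0.3% | 2.7% |
| Both conditions, top dose only at 0.67 of proportional | 7% | 35% | 55% | 67% |

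The second row is the same for 30-, 100- and 300-fold ranges, because a shortfall at one dose does not grow with the range. A wide Part A range therefore protects against a constant slope error but not against this pattern.

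**Example.** Take Part B at CV 30% with an observed slope of 1.25. The expected CI is 1.25 ± 0.259, or 0.99 to 1.51. The implied departure is 4^0.25 = 1.41-fold, with CI 4^(−0.009) = 0.99 to 4^0.509 = 2.03. Data compatible with a doubling of dose-normalised exposure would be concluded 'dose proportional', provided linearity was accepted.

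**The case against.** The case for leaving the rule alone has five parts.

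- **The reader sees the evidence anyway.** The SAP already reports the slope, its CI, the CV, log-log plots against the proportionality line, and dose-normalised plots and summaries. SAP 8.1 adds a general caution. This is true, and it is why the remedy is cheap. But the prespecified conclusion stays the same however wide the CI is.
- **The simulation simplifies the linearity check.** It uses the p-value alone, whereas plots must also look reasonable and the visual review could reject a model with an obvious top-dose shortfall. This stands: the joint percentages describe the numerical part of the rule only. The visual review has no stated criterion and can also work the other way.
- **The numbers depend on assumptions.** With doses 1:3:9 and slope 0.7, the CI spans 1 in 0, 5, 21 and 38% of trials, against 7, 37, 58 and 70% for 1:2:4. The total departure is also larger there (9^(−0.3) = 0.52). Optional groups B4 to B6 would add precision. Protocol 1.7 gives a direction in animals but no size; the 0.67 is an assumption. All of this stands, but the logical fault does not depend on any of these values.
- **Little hangs on it.** Safety is the primary objective, dose proportionality is not a named objective or endpoint, and escalation does not use this verdict. This limits the importance. It also argues for descriptive wording over a yes/no verdict.
- **A strict equivalence test is out of reach.** For Part B with 1:2:4 and slope exactly 1, a 95% CI falls within 0.8–1.25 limits in 7% of trials or fewer over the assumed CVs. This is why no margin is proposed below.

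**Conclusion.** The concern holds. The SAP prespecifies a positive conclusion from a non-significant result, and nothing else in the protocol or SAP corrects it. At moderate variability (CV 30 to 50%), roughly one third to two thirds of trials would meet both numerical conditions despite a 1.5-fold departure over a 4-fold range in Part B, or a one-third shortfall at the top dose in Part A. Those rates rest on the assumed CVs, dose spacing and departures, and on the lack-of-fit p-value alone deciding linearity. At CV 20% they fall to about 7%, and constant-slope departures over a wide Part A range are nearly always detected. The consequence is confined to how a secondary PK analysis is reported. It should be fixed, but it does not touch the primary safety objective or escalation.

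**What to change.** Replace the verdict sentence in SAP 8.5.3.1 with:

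> The slope, its CI and the implied fold departure from proportionality over the dose range studied, r^(slope − 1) with its CI (r = highest/lowest dose), will be reported. A CI that includes 1 will be described as no evidence against proportionality, not as proof of it.

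Where the visual assessment overrides the lack-of-fit test, report both results.

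If a yes/no conclusion is wanted, require the whole CI to lie between 1 + ln(θL)/ln(r) and 1 + ln(θU)/ln(r). Fix θL and θU before unblinding, justify them as the largest acceptable departures, and allow an inconclusive outcome otherwise. The choice is not trivial. Limits of 0.5–2.0 tolerate the 1.5-fold departures at issue: in Part B with slope 1.3 the 95% CI falls inside them in 63, 34, 21 and 13% of trials at CV 20, 30, 40 and 50%. Limits of 0.8–1.25 are almost unattainable with 18 subjects at these CVs.

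One clarification belongs in the same edit. The Part A analysis is described as "on profile day 1 for Part A", but Group A3 has a Day 1 in both the fasted and the fed period, and the example power-model code has no subject or treatment term. State that the model uses fasted records only, one per subject.

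The cost is SAP wording and one quantity derived from an estimate already planned. The downside is fewer definitive statements of proportionality.
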